#### **10.3.5.1 Summary Statistics**

For the treatment phase of the trial, for the safety cohort, mean change and mean percentage (%) change from baseline to the end of trial will be presented for each vital signs variable. In addition, descriptive statistics, i.e., the number of subjects with data, mean (standard deviation), median, minimum, and maximum values, will be presented for observed values and change from baseline at each time-point for each vital signs variable.

#### **10.3.5.2 Notable Changes in Vital Signs**

Summary tables will be prepared displaying the number and percentage of subjects with normal baselines who had one or more pre-specified notable treatment-emergent values, according to the definition in [Appendix 1](#).

#### **10.3.5.3 Data Listings**

Data listings will be prepared by centre for all subjects with any notable vital signs value at any time-point (including screening, baseline).

### **10.4 Other Safety Variables**

#### **10.4.1 Bleeding Log Assessment**

At the start of PVR, each subject will receive a bleeding log. For each incidence of sanitary napkin use for bleeding/spotting, subjects will be instructed to record the date, time of day, and the severity of the bleeding. For each subject, for each day: the grade (intensity) of bleeding associated with each sanitary napkin use will be summed. The sum of the daily grades (intensity) of bleeding will be averaged by visit window (see [Table 4](#)) where the visit window will cover the subject's Bleeding Log recording period (i.e., from the start of the PVR to the End-of-trial visit). Finally, this subject data will be summarized across all subjects for the safety cohort by visit window. The summary will include mean, median, standard deviation, minimum and maximum.

The analysis outlined above will be repeated removing the date of fresh transfer, periods associated with AEs reported as vaginal hemorrhage, the primary endpoint of spontaneous abortion and information collected after the cessation of the use of PVR. For vaginal hemorrhaging, spontaneous abortion and biochemical abortion, this will be achieved by removing bleeding log assessment collected starting from two days prior to the start of such an event up to two days after the end of such an event. Furthermore, for subjects with any negative  $\beta$ -hCG result, the bleeding log assessment will be summarized.

For subjects that discontinue from PVR early, the bleeding logs will be calculated normally (as per [Table 4](#)) until PVR is discontinued. Bleeding log entries after the visit preceding the Early Withdrawal Visit and bleeding log entries after PVR is withdrawn will be assigned to Visit 9. At the end of study visit and beyond, bleeding log entries will be assigned to Visit 10.

**Table 4** Visits numbers, nominal visit days from oocyte retrieval date and associated visit windows

Visit	Nominal visit date from date of oocyte retrieval (Day 1= date of oocyte retrieval)	Visit window (Day 1= date of oocyte retrieval)
Visit 3	Day 1	
Visit 4	Day 2	Start of IMP - Day 3
Visit 5	Day 5	Day 4 – Day 9
Visit 6	Day 14±1	Day 10 – Day 15
Visit 6P	Day 17±1	Day 16 – Day 19
Visit 7	Day 21±1	Day 20 – Day 26
Visit 7P	Day 31 ±1	Day 27 – Day 36
Visit 8	Day 42±1	Day 37 – Day 56
Visit 9	Day 70±1	Day 57 – Day 77
Visit 10	Day 84	Day 78 – Day 90

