7.2.4 Bleeding Log

Vaginal bleeding will be recorded in a Bleeding Log by the subject ([Appendix 4](#)). The subject will be instructed to use only sanitary napkins provided by the trial site for any bleeding/spotting that occurs during the trial; tampons are not permitted. This Bleeding Log will be given to all subjects at Visit 4 to capture the incidence (frequency and intensity) of any vaginal bleeding/spotting occurring throughout the trial i.e. until end-of-trial. For each incidence of bleeding/spotting, subjects will be instructed to record the date, time of day (AM versus PM), and the severity of the bleeding using a Pictorial Blood Loss Assessment chart ([Wyatt, 2001](#)). The grade (intensity) is scored as shown in [Appendix 5](#).

Bleeding deemed clinically significant in the opinion of the Investigator will be reported as an AE.

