9.9.5 Bleeding Log

At the start of PVR, each subject will receive a bleeding log (see section [8.3](#) and [Appendix 4](#)). For each incidence of sanitary napkin use for bleeding/spotting, subjects will be instructed to record the date, time of day, and the severity of the bleeding. For each subject, for each day: the grade (intensity) of bleeding associated with each sanitary napkin use will be summed. The sum of the daily grades (intensity) of bleeding will be averaged by visit window where the visit window will cover the subject's Bleeding Log recording period (i.e., from the start of the PVR to the End-of-trial visit). Finally, this subject data will be summarized across all subjects for the safety cohort by visit window. The summary will include mean, median, standard deviation, minimum and maximum. Furthermore, this analysis will be repeated removing the periods associated with AEs reported as vaginal hemorrhage, the primary endpoint of spontaneous abortion, the secondary endpoint of biochemical abortion and information collected after the cessation of the use of PVR.

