Appendix 5 Scoring of Bleeding Log Information

Napkin	Grade
	1
	2
	3
	4
	5

Adapted from: Wyatt KM, Dimmock PW, Walker TJ, O'Brien PM. Determination of total menstrual blood loss. Fertil Steril. 2001;76(1):125-31.

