## Secondary Endpoints

- Cumulative rate of spontaneous abortions determined at 6 and 10 weeks post-oocyte retrieval in all subjects treated with PVR.
- Cumulative rate of biochemical abortions determined at 6 and 10 weeks post-oocyte retrieval in all subjects treated with PVR. Biochemical abortion is defined as a positive  $\beta$ -hCG test at 2 weeks and 2 weeks + 3-4 days post-oocyte retrieval, but followed by no observed gestational sac on a later TVUS, or followed by a negative  $\beta$ -hCG test.
- Rate of ectopic and heterotopic pregnancies in all subjects treated with PVR following oocyte retrieval.
- Rate of abnormal findings in clinical laboratory tests and vital signs for all subjects treated with PVR.
- Frequency, intensity/grade, seriousness, and relatedness of adverse events (AEs) for all subjects treated with PVR.
- Frequency, intensity/grade of vaginal bleeding/spotting, vaginal hemorrhage, pain, vaginal infection, and vaginal irritation for all subjects treated with PVR.
- Frequency, intensity/grade, seriousness, and relatedness of AEs associated with vaginal and cervical abrasions and lesions and with vaginal adhesions for all subjects treated with PVR.
- Frequency and reason for PVR discontinuation.
- Positive  $\beta$ -hCG rate (positive serum  $\beta$ -hCG test) at 2 weeks and 2 weeks + 3-4 days post-oocyte retrieval in all subjects treated with PVR.
- Clinical pregnancy rate (TVUS showing at least 1 intrauterine gestational sac with fetal heartbeat) at 6 and 10 weeks post-oocyte retrieval in all subjects treated with PVR.

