### **10.2.3 Treatment-Emergent AEs of Special Interest**

Standardized criteria will be applied to some AEs of special interest to establish intensity/grade. For AEs associated with vaginal bleeding/spotting, vaginal pain and irritation, and vaginal or cervical abrasions and lesions, standardized criteria will be used by the sites to record the intensity of these AEs (Protocol Section 8). For these AEs and AEs associated with vaginal hemorrhage, vaginal infection and vaginal adhesions, a summary table of the treatment-emergent AEs of special interest will be produced by preferred term, grade (intensity), and seriousness for subjects in the safety cohort for the treatment phase and the study phase. These AEs will be identified using preferred terms.

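### The planned bleeding-log summary does not show how many women bled, on how many days or at what worst grade; only bleeding judged clinically significant is counted, through the AE tables

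*SAP*

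**What the plan says.** The secondary endpoints in SAP 2.2 (and Protocol 2.2) include "Frequency, intensity/grade of vaginal bleeding/spotting, vaginal hemorrhage, pain, vaginal infection, and vaginal irritation for all subjects treated with PVR". Protocol 7.2.4, which stands under the assessments related to secondary endpoints, gives every woman a log at Visit 4 "to capture the incidence (frequency and intensity) of any vaginal bleeding/spotting occurring throughout the trial". Each napkin is graded 1 to 5 (Protocol Appendix 5).

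The analysis is in SAP 10.4.1. For each woman and day, "the grade (intensity) of bleeding associated with each sanitary napkin use will be summed". Then "The sum of the daily grades (intensity) of bleeding will be averaged by visit window", with the windows in SAP Table 4. The across-subject display is the same in both documents; in the words of Protocol 9.9.5, "The summary will include mean, median, standard deviation, minimum and maximum". The analysis is repeated with certain periods removed, using the same reduction. A further summary for women with a negative β-hCG is mentioned without its content. Neither section mentions a count of women who bled, a count of bleeding days, a distribution of grades or a listing.

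The plan has two other routes to bleeding data:

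- **AE tables.** Protocol 7.2.4 says: "Bleeding deemed clinically significant in the opinion of the Investigator will be reported as an AE". SAP 10.2.3 covers bleeding/spotting AEs and says that "a summary table of the treatment-emergent AEs of special interest will be produced by preferred term, grade (intensity), and seriousness". The AE tables in SAP 10.2.2 give subjects, percentages and events.
- **Hemorrhage.** SAP 10.4.2 counts women with vaginal hemorrhage from a dedicated eCRF module.

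**The concern.** The endpoint asks two plain questions about bleeding and spotting in all treated women: how often, and how severe. The log collects what is needed to answer both. The planned score then merges three quantities: the number of napkins, the number of days and the grade per napkin. Averaging over a window, and again over women, removes the means of separating them.

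Bleeding below the investigator's threshold of clinical significance does not reach the AE tables. For that bleeding, the log summary is the only planned output. If it cannot say how many women bled, the report will be silent on the frequency of minor bleeding and spotting on the ring, in a safety trial where local tolerability is a stated interest.

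**Working it through.** The documents give no figure for the bleeding log, so there is no stated result to reproduce. The check asks whether the planned statistics determine the quantities named in the endpoint. A counterexample is enough to show that they do not.

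**Inputs from the documents**
- Napkin grades 1 to 5: Protocol Appendix 5.
- Visit 8 window, Day 37 to Day 56: 56 − 37 + 1 = 20 days (SAP Table 4). The longest window is Visit 9, Day 57 to Day 77: 21 days.
- Across-subject statistics: mean, median, SD, minimum, maximum (SAP 10.4.1).

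**Assumptions**
- N = 240, the planned mITT size. The log is summarized for the safety cohort, whose size is not stated.
- Days without an entry count as zero, so the divisor is 20. The SAP does not say this.
- The numbers of bleeders are illustrative. The documents give no expected rate.

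**Step 1: one woman.** Window score = (sum of napkin grades in the window) / 20.
- One grade 1 napkin on each of 10 days: 10 × 1 / 20 = 0.5.
- Two grade 5 napkins on a single day: 2 × 5 / 20 = 0.5.

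Ten days of the lightest grade and one day of the heaviest give the same score. If the average runs only over days with entries, the same two women score 10/10 = 1 and 10/1 = 10. The choice of denominator therefore changes the result, and it is not stated.

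**Step 2: two cohorts of 240.** Summed grades per woman over the window:

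| | Women with a non-zero sum | Bleeders | Total | Sum of squares |
|---|---|---|---|---|
| A | 20 at 4, 20 at 5, 1 at 10 | 41 (17.1%) | 80 + 100 + 10 = 190 | 320 + 500 + 100 = 920 |
| B | 20 at 1, 20 at 2, 20 at 6, 1 at 10 | 61 (25.4%) | 20 + 40 + 120 + 10 = 190 | 20 + 80 + 720 + 100 = 920 |

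The totals and sums of squares are equal, so the mean and SD must be equal:
- Mean = 190 / 240 / 20 = 0.0396 in both.
- SD = √[(920 − 190²/240) / 239] / 20 = √3.220 / 20 = 0.0897 in both.
- Median = 0 in both, since fewer than half bled. Minimum = 0. Maximum = 10/20 = 0.5.

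All five planned statistics agree, while the number of women who bled differs by 20.

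**Step 3: a second pair.** Replacing each 20 by 35 gives 71 (29.6%) and 106 (44.2%) bleeders. Both cohorts have total 10 + 35 × 9 = 325 and sum of squares 100 + 35 × 41 = 1535. Both give mean 0.0677, median 0, SD 0.1070, minimum 0 and maximum 0.5.

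**Step 4: what the missing display would show.** For assumed counts of women with any logged bleeding, the exact (Clopper-Pearson) 95% intervals are:
- 24/240 = 10.0% (6.5 to 14.5)
- 60/240 = 25.0% (19.7 to 31.0)
- 120/240 = 50.0% (43.5 to 56.5)

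**The case against.** The strongest reply is that the endpoint is served elsewhere. Protocol 3.5.2 describes AEs of special interest, bleeding/spotting among them, as secondary endpoints. Their frequency and grade are tabulated, and hemorrhage is counted. This stands. A reader might infer that the bleeding endpoint is not estimated at all, and the documents do not support that. The gap is bleeding that was logged but not reported as an AE.

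The AE route also has limits. The special-interest AEs are identified by preferred term, and the list in SAP Appendix 3 has vaginal haemorrhage but no separate bleeding or spotting term. No mapping is given from napkin grades 1 to 5 to AE grades 1 to 4.

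A second reply is that the five statistics do carry information. This also stands. The score reflects amount and duration together, and a median above zero would mean that at least half the women bled. A reader might infer that widespread light spotting and heavier bleeding in a few women always look the same, which is too strong. Suppose 15% of women bleed on 3 days at a daily score of 2, or 45% bleed on 1 day at the same score. Both give mean 0.045 and median 0, but the maximum is 6/20 = 0.30 against 2/20 = 0.10, and the SD about 0.107 against 0.050. The planned table would show that contrast. The valid claim is that the statistics do not identify the number of bleeders, as Step 2 shows.

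A third reply is that in a descriptive trial, judged on the totality of safety information, the choice of summary is a matter of taste. That is a fair argument against demoting the mean score, and nothing here requires it. It does not explain why a listed frequency has no count.

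**Conclusion.** The planned log summary cannot give the number of women with any bleeding or spotting, their bleeding days or their worst grade. No other planned output gives these for bleeding below the clinical-significance threshold. For clinically significant bleeding and for hemorrhage, counts are planned.

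The size is shown by example: 17.1% and 25.4% of women bleeding, or 29.6% and 44.2%, can produce identical tables. That is roughly a 1.5-fold difference in frequency. These figures rest on the assumed N of 240, the 20-day window, zero for days without an entry and chosen score patterns. They are not predictions of what the trial will find. The conclusion itself does not depend on the chosen values, because mean, median, SD, minimum and maximum do not fix the number of non-zero observations.

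The unstated denominator is a separate, smaller defect, since it leaves the planned score itself open to two readings. Both should be put right, but neither touches the primary analysis.

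**What to change.** In SAP 10.4.1 add three displays, per visit window and overall while on the ring:

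1. Number and percentage of women with at least one logged bleeding day, with an exact 95% CI.
2. Bleeding days per 7 observed days.
3. Distribution of each woman's worst napkin grade.

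State that the daily average runs over all observed days in the window, that a day without an entry in an available log counts as zero, and that periods with no log available are missing. Keep the planned mean-score summary alongside.

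The addition does not conflict with Protocol 9.9.5, and the displays use log entries already planned. The cost is a few descriptive tables over nine windows plus the overall period. One condition must be checked first. Women are asked to bring the log to each visit (Protocol 6.3.1), but the documents describe no data field recording whether it was returned. Log availability has to be identifiable in the data for the zero and missing rules to work.

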3.5.5 Selection and Timing of Dose for Each Subject

A new PVR will be inserted every 7 days, with up to 10 PVRs used through Week 12 of pregnancy (10 weeks post-oocyte retrieval).

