## Change log

Version No.	Effective Date	Reason for the Change / Revision	Supersedes
1.0	May 11, 2018	NA	None
2.0	Oct 08, 2018	

• To make the SAP consistent with the protocol amendment.

• More detailed analysis of embryo quality has been added.

• More details have been added to the analysis of bleeding logs.

• Typographical and formatting errors have been corrected.

	1.0
3.0	Feb 26, 2019	

• Responded to FDA feedback on statistical design by adjusting confidence intervals and assuring that endpoints align with the DR-PGN-302 study

• Updated the document author to reflect the new statistician

• Corrected formatting issues, typos, text relating to which drug was used for hCG triggering, and “Other Endpoint(s)” to “Other Assessment(s)”

• Added tabulation of vaginal hemorrhage (was in protocol, but not SAP)

• Clarified the use of Preferred Terms, how baseline is calculated for laboratory and vital signs variables, how shift tables are to be calculated, and the tabulation of bleeding log data for non-completers.

	2.0

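### SAP 10.4.1 reports early discontinuers' post-ring bleeding under Visit 9 (Days 57–77) whatever its date; after a negative hCG test those entries fall on about Days 16–35

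*SAP*

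**What the plan says.** SAP 10.4.1 sums the bleeding grades for each day, averages the daily sums within visit windows for each woman, and summarises the result over the safety cohort by window. Table 4 sets the windows, with Day 1 as the day of oocyte retrieval. Visit 9 is Days 57–77 and Visit 10 is Days 78–90. Protocol 9.9.5 describes the same summary, in which daily sums "will be averaged by visit window where the visit window will cover" the log recording period, and mentions no reassignment.

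For early discontinuers the SAP adds three rules:

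- Up to ring discontinuation, "the bleeding logs will be calculated normally", that is, by Table 4.
- Entries after the visit that precedes the Early Withdrawal Visit go to Visit 9, and "bleeding log entries after PVR is withdrawn will be assigned to Visit 9".
- A parallel rule covers the close of the log: "At the end of study visit and beyond, bleeding log entries will be assigned to Visit 10".

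The second and third rules carry no date condition. The SAP change log for version 3.0 lists "the tabulation of bleeding log data for non-completers" among its clarifications.

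Two further outputs are planned. One is a repeat: "The analysis outlined above will be repeated removing the date of fresh transfer", together with other periods, including everything after ring cessation. The other covers women with any negative hCG result, for whom "the bleeding log assessment will be summarized"; no windowing is stated for it.

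**The concern.** A negative hCG test ends treatment two to three weeks after retrieval, and the log then closes at an End-of-trial visit about two weeks later (Protocol 3.5.6 and 6.4). None of that bleeding can fall on Days 57–77. Under the rule it is nevertheless averaged into the Visit 9 row, beside entries from women still pregnant around Week 10.

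Frequency and grade of vaginal bleeding/spotting is a listed secondary endpoint (Protocol 2.2, SAP 2.2). A reader of the main table would take the Visit 9 row as bleeding in Days 57–77, when part of it is bleeding after a failed cycle weeks earlier.

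The second rule also overlaps the first. For a woman who stops between visits, on-ring entries after her last visit belong to Table 4 by one sentence and to Visit 9 by the next. Two programmers could produce different tables.

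**Working it through.** **Inputs.** Visit 6 is 14±2 days after retrieval (Protocol 6.3.3), Visit 6P is 3–4 days after Visit 6 (6.3.4), and Visit 7 is 21±2 days after retrieval (6.3.5). End-of-trial is 14±2 days after last exposure (6.4). The log runs to the End-of-trial visit (Table 6-1, note e). The windows are those of SAP Table 4.

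**Assumption.** The ring is removed on the day of the negative test.

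**Formulas.** Day = days after retrieval + 1. Entries sent to Visit 9 run from removal day + 1 to End-of-trial day − 1. Brackets show the range with all tolerances.

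| Negative test at | Ring out | End-of-trial | Entries sent to Visit 9 |
|---|---|---|---|
| Visit 6 | Day 15 (13–17) | Day 29 (25–33) | Days 16–28 (14–32) |
| Visit 6P | Day 18–19 (16–21) | Day 32–33 (28–37) | Days 19–32 (17–36) |
| Visit 7 | Day 22 (20–24) | Day 36 (32–40) | Days 23–35 (21–39) |

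**Log days per woman.** 14 − 1 = 13, with a range of 12 − 1 = 11 to 16 − 1 = 15.

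**Distance from the Visit 9 window.** The latest nominal entry is 57 − 35 = 22 days early and the earliest is 57 − 16 = 41 days early. With every tolerance at its limit the smallest gap is 57 − 39 = 18 days. Each day of delay in removing the ring moves the dates one day later and shortens the gap by a day.

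**Where the entries belong by date.** Table 4 lists Visits 6 and 7 at nominal Days 14 and 21, although counting retrieval as Day 1 gives Days 15 and 22. The split depends on which is used:

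| Negative test at | Convention | Visit 6 | Visit 6P | Visit 7 | Visit 7P | Visit 9 |
|---|---|---|---|---|---|---|
| Visit 6 | Retrieval + 1 (Days 16–28) | 0 | 4 | 7 | 2 | 0 |
| Visit 6 | Table 4 nominal (Days 15–27) | 1 | 4 | 7 | 1 | 0 |
| Visit 7 | Retrieval + 1 (Days 23–35) | 0 | 0 | 4 | 9 | 0 |
| Visit 7 | Table 4 nominal (Days 22–34) | 0 | 0 | 5 | 8 | 0 |

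Each row sums to 13, and none of the days lies in Visit 9 on either convention.

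**Later discontinuers.** A stop at Visit 7P gives post-ring entries at about Weeks 4.5–6.5, and a stop at Visit 8 at about Weeks 6–8. They go to the same row.

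**Visit 10.** End-of-trial falls on Days 29–36 (25–40), before the window by 78 − 36 = 42 days or more at nominal timing (78 − 40 = 38 with tolerances). Because the log closes at that visit, this concerns about one log day per woman.

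**Conflict for on-ring entries.** Take a woman seen at Visit 8 (Day 43) who stops before Visit 9. Table 4 puts her entries up to Day 56 in Visit 8; the next sentence puts them in Visit 9. The overlap is at most Days 44–56, that is 56 − 43 = 13 days at nominal timing. It reaches that only if she is still on the ring at Day 56.

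**Completers.** The ring is used "with up to 10 PVRs used through Week 12 of pregnancy", so the last one comes out on Day 71 or 72. That leaves 77 − 71 = 6 or 77 − 72 = 5 off-ring days among the 21 in the Visit 9 window.

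**The case against.** The strongest defence is that the rule is deliberate and follows the protocol's own labels. Protocol 6.3.8 combines Visit 9 with the Early-withdrawal Visit, and Visit 10 is the End-of-trial visit whenever it occurs. Protocol section 9 leaves analysis detail to the SAP, so Protocol 9.9.5 is not contradicted. This explains the rule. It suits assessments made at those visits, but not a dated daily log averaged and read by day window.

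The plan also has cleaner outputs. The repeat analysis drops post-ring entries, women with a negative test get their own summary, and bleeding is tabulated by grade among the adverse events of special interest. These limit the harm but do not correct the main table. The repeat can also keep on-ring entries that the Visit 9 clause has moved.

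The conflict between the two sentences is narrow, and this stands. When the ring is stopped at a scheduled visit the clauses coincide. They diverge only for women who stop between visits, a number the documents do not give.

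Keeping post-ring bleeding after a failed cycle out of the early on-ring rows is also defensible, and the fix below keeps it so. The fault is the false late label.

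A reader might infer that the Visit 10 row is as badly affected as Visit 9, or that Visit 9 would otherwise be a purely on-ring row. Neither is supported: Visit 10 gains about one day per woman, and completers already contribute 5–6 off-ring days to Visit 9.

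**Conclusion.** The point holds. As written, the Visit 9 row of the main bleeding-log summary is not a summary of Days 57–77. Each woman stopped after a negative hCG test adds about 13 post-ring log days (11–15) from roughly Days 16–35, about three weeks or more before the window opens. That rests on removal on the test day; delay moves the dates later. Later discontinuers add entries from about Weeks 4.5–8. The Visit 10 rule has the same flaw on a minor scale, and the on-ring conflict affects an unknown number of women.

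It is tempting to conclude that the table will overstate late bleeding or hide early bleeding by some amount. The documents do not support either. They give no negative-test rate, no expected bleeding scores, no rule for days without an entry, and no statement of whether a reassigned spell is averaged over its own days or over the 21-day window. Size and direction therefore cannot be derived. The summary is descriptive, and the primary endpoint and adverse-event tables are unaffected. The change should be made, but it concerns one table.

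**What to change.** In SAP 10.4.1, for early discontinuers:

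- Assign on-ring entries by actual date to the Table 4 windows, up to the day the ring is withdrawn. Delete the clause about entries after the visit preceding the Early Withdrawal Visit.
- Report all post-ring entries, including any at or after the End-of-trial visit, in one separately labelled row, *post-PVR / early withdrawal*, instead of Visit 9 or Visit 10.
- State that the repeat analysis and the negative-hCG summary use the same rule.

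Completers stay on Table 4 as now.

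This makes the Visit 9 and Visit 10 rows true to their windows, removes the conflict between the two sentences, and keeps off-ring bleeding out of the early on-ring rows. It does not return post-ring entries to the early windows in which they occurred; it shows them openly in their own row. The log is dated, so no new data are needed. The cost is SAP wording, programming and one extra table row.
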